PASS information

Title	Study of utilisation of combined hormonal contraceptives in Europe
Protocol version identifier	1.1
Date of last version of protocol	06 april 2017
EU PAS register number	Study not registered
Active substance	Not applicable
Medicinal product	Not applicable
Product reference	Not applicable
Procedure number	Not applicable
Marketing authorisation holder(s)	Not applicable
Joint PASS	No

Research question and objectives	
Was there a change in CHC prescribing patterns between the periods January 2012 – January 2014 and February 2014 – December 2015 and, if so, was there a subsequent change in the incidence rate of VTE?
 
Objectives
 
 1. To investigate trends in new user (initiators) prescribing patterns in the two years preceding the relevant Commission Decision (January 2012 – January 2014) and in a similar period following the decision (February 2014– December 2015). 2. To investigate switching patterns between products among prevalent users including reasons for changes (e.g., reimbursement or regulatory and clinical guidance). 3. Within Objectives 1 and 2, to examine any changes in utilisation in groups defined by patient’s clinical and demographic risk factors for VTE as detailed in the warnings and contraindications in the European Union Summary of Product Characteristics (SmPC). 4. To examine any differences in the incidence rates of VTE between the two periods specified and, in light of the results for Objective 1-3, to investigate any measurable association between the observed changes in CHC use and changes in the VTE incidence rates.
Country(-ies) of study	The Netherlands, Denmark, United Kingdom
Author	[name] Email: [contact]

Contents

PASS information	1
1. Marketing authorisation holder(s)	4
2. List of abbreviations.....	5
3. Responsible parties	6
4. Abstract	7
5. Amendments and updates	13
6. Milestones	13
7. Rationale and background.....	14
8. Research question and objectives	14
9. Research methods	15
9.1 Study design	15
9.2 Data collection and analysis.....	17
9.3 Data management.....	25
9.4 Quality control	25
9.5 Limitations of the research methods	26
10. Protection of human subjects	26
11. Plans for disseminating and communicating study results	26
12. References	26

1. Marketing authorisation holder(s)

Marketing authorisation holder(s)	Not applicable
MAH contact person	Not applicable

2. List of abbreviations

CHC	Combined hormonal contraceptives

It is unknown whether the publication of the review has led to a change in prescribing patterns and a subsequent change in the incidence of VTE. Therefore, we want to investigate the CHC prescribing patterns among women in three European Union Member states (the Netherlands, Denmark and the United Kingdom) in a time period including the completion of the 2013 review and implementation of the resulting recommendations and to estimate any changes in the incidence of VTE between the two periods specified.

Risk of developing a blood clot (VTE) in a year	
Women not using a combined hormonal pill/patch/ring and are not pregnant	About 2 out of 10,000 women
Women using a CHC containing levonorgestrel, norethisterone or norgestimate	About 5-7 out of 10,000 women
Women using a CHC containing etonogestrel or norelgestromin	About 6-12 out of 10,000 women
Women using a CHC containing drospirenone, gestodene or desogestrel	About 9-12 out of 10,000 women
Women using a CHC containing chlormadinone, dienogest or nomegestrol	Not yet known ¹

¹ Further studies are ongoing or planned to collect sufficient data to estimate the risk for these products.

Research question

Was there a change in CHC prescribing patterns between the periods January 2012 – January 2014 and February 2014 – December 2015 and, if so, was there a subsequent change in the incidence rate of VTE?

Objectives

1. To investigate trends in new user (initiators) prescribing patterns in the two years preceding the relevant Commission Decision (January 2012 – January 2014) and in a similar period following the decision (February 2014 – December 2015).
2. To investigate switching patterns between products among prevalent users including reasons for changes (e.g., reimbursement or regulatory and clinical guidance).
3. Within Objectives 1 and 2, to examine any changes in utilisation in groups defined by patient's clinical and demographic risk factors for VTE as detailed in the warnings and contraindications in the European Union Summary of Product Characteristics (SmPC)(2).
4. To examine any differences in the incidence rates of VTE between the two periods

specified and, in light of the results for Objective 1-3, to investigate any measurable association between the observed changes in CHC use and changes in the VTE incidence rates.

Study design:

Using data retrieved from electronic health records (see below: Data sources) from three European Union member states, i.e. the Netherlands, Denmark, and United Kingdom, we will address the study objectives in

1. A drug utilization study into prescribing patterns including new use of CHCs and calendar-period specific changes in switching of CHCs
2. A cohort study for incidences of VTE

Population, Variables and Data sources:

For the Dutch drug utilization study and cohort study, we will make use of de-identified data obtained through The Dutch Foundation for Pharmaceutical Statistics (SFK), which gathers its data from >95% of community pharmacies in the Netherlands (<https://www.sfk.nl/english>). All women between the ages of 18-49 years with at least one prescription of combined oral contraceptive use in the period from January 2012 through December 2015 will be included, i.e., both new users as well as prevalent users. New users are defined as women who do not have a prescription of CHC in the two years before starting. We will also obtain information on prevalent users of CHC and thereby we can assess all individual changes (switches) in CHC. Prevalent users of CHC are defined as women who used at least one cycle of CHC. Age at initiation and 4 digit postcodes is also available in the SFK database which allows further characterization of CHC users by age and socioeconomic status. The latter information will be retrieved by using information from the Central Bureau of Statistics (CBS), the Netherlands, which keeps record of socioeconomic status by use of 4-digit postcodes. Although SFK does not indicate if women had venous thrombotic disease for which they need to receive anticoagulant treatment, it can be approximated by the first dose of oral anticoagulant (direct oral anticoagulant (DOAC)) or duration of anticoagulant (vitamin K antagonist), which is specific for VTE.

For the Danish drug utilization and cohort study, data will be linked from the following databases: The Danish Civil Registration System (contains data on age, sex, vital status and migration), the Danish National Prescription Registry (outpatient dispensations of CHC and other

medications), and data on income and education at Statistics Denmark. Women between the ages 18-49 years in the period January 2012- December 2015 will be included, i.e. both new and prevalent users.

For the UK drug utilization and cohort study, we will make use of anonymised primary care data. In the period January 2012- December 2015, women between the ages 18-49 years who have been registered for at least two years prior with one of the general practices that contributed data to The Health Improvement Network (THIN) primary care database will be included. New and prevalent users will be identified. In addition, information is available on social deprivation, body mass index (BMI) and smoking status which can be used to stratify patients on the risk of VTE.

Study size:

In 2014, approximately 1.4 million women between 15-50 years used oral contraceptives in the Netherlands, of whom ~1.3 million are registered in the SFK. In women between 15-25 years, the majority of oral contraceptive users will be starters (the new users in our study will include these starters as well as women who have used CHC in the past, but not in the previous two years). Data from the CBS indicated, that in 2014, there were 1 011 127 women between 15-25 years, of whom ~59% were using oral contraceptives (n=596 565). From unpublished data from the department of Clinical Epidemiology, Leiden University, we estimate that in 2-year period, approximately 16% of premenopausal women switch from one oral contraceptive agent to another. With 1.3 million oral contraceptive users, this indicates ~212 000 switches per 2-year period.

As mentioned above, the number of women between 15-25 years using CHCs in 2014 is 596 565. This number will vary in the other years of the study period. From literature it is known that the risk of VTE is increased 8-fold among starters in the first year of use (in the first three months, the risk is increased 13x) (3). However, this risk differs for the different types of CHCs. Also the proportion of each generation of CHC will differ in each observation window. Therefore, it is difficult to estimate the number of cases of VTE in new users of CHC in the study period January 2012- December 2015.

In Denmark, annually more than 330 000 women receive CHC (<https://laegemiddelstyrelsen.dk/da/udgivelser/2016/~-/media/CD29697BD25C4642968D9386979472A9.ashx>; <http://medstat.dk/>). The annual incidence rate of VTE is about 4 per 10 000 for women of reproductive age not using oral contraceptives. Thus, a conservative estimate for 4 years of follow-up assuming the size of the study population of 300 000, is at least 480 cases of

VTE (4).

A previous UK primary care database study estimated the crude incidence rate of VTE cases per 10 000 women years was 5.9 (95% confidence interval 5.7-6.0) in CPRD and 6.1 (6.0- 6.3) in QResearch (5). In UK around 28% use oral contraceptives and CHC form a substantial proportion of these.

Data analysis:

In order to assess the effects of the review on initiation (new use) as well as on switching of treatment (between January 2012- January 2014 and between February 2014- December 2015), we will perform segmented regression analyses.

For the Dutch part of study, we will calculate the incidence of VTE among the new users of CHC within each calendar window (January 2012- January 2014 and February 2014- December 2015). From segmented regression analysis, we will obtain information on a potential change in the proportion of different types of oral contraceptives in new users separately and grouped according to generation of CHC after the European commission decision (January 2014). Since we have information about the prescription patterns among new users, we can assess whether the changes observed in the proportions of use of each generation is associated with changes in the incidence rate of VTE in women initiating oral contraceptive use. Furthermore, we will study the changes in the incidence of VTE within users of different types (and generations) of CHCs. A change in this incidence over time, may indicate that certain preparations are prescribed to low/high risk individuals. We will stratify analyses on age and socioeconomic status (risk factors of VTE) of the women.

For the Danish and UK part of the study, estimates on the incidence of VTE will be calculated. Overall estimates as well as estimates stratified by risk factors such as age, socio-economic status, BMI (UK only), smoking status (UK only) will be provided. For the Danish and UK data we will compare the age-standardised incidence rates of VTE against the age standardised initiations of oral contraceptives in order to evaluate whether overall changes in CHC use is associated with overall changes in incidence of VTE.

Milestones:

Task	Month
Data extraction and analysis	10
Writing study results for the EMA	3
Writing manuscript for submission to peer-reviewed journal	3

5. Amendments and updates

None

6. Milestones

Milestone	Planned date
Start of data collection (extraction)	31-03-2017
End of data collection (extraction)	31-12-2017
Final report of study results	01-05-2018
Delivery of manuscript	01-05-2018

7. Rationale and background

Venous thromboembolism (VTE) in young women is rare, with an annual incidence of approximately 2-5 per 10 000 women (6). An increased risk of VTE associated with oral contraceptive use has long been established and while the absolute risk of VTE in young women is low, the fact that millions of women worldwide are using oral contraceptives indicates that these preparations are responsible for a large number of cases of VTE

(3, 7-11). Several large studies including a review in 2013 by the European Medicines Agency (EMA) concluded that the risk of VTE associated with hormonal contraceptive preparations which contained gestodene, desogestrel, or drospirenone was increased compared with hormonal contraceptive preparations containing levonorgestrel (1, 5, 12, 13).

After the publication of the review by the EMA, the European Commission adopted on 16 2014, a legally binding decision to update the product information of all combined hormonal contraceptives (CHC) throughout the European Union. This included information to patients: awareness of factors that increase the risk of VTE and information to health care professionals: the type of CHC with the lowest VTE risk (levonorgestrel, norethisterone, or norgestimate) and the fact that CHC are contraindicated in the presence of one serious or multiple risk factors for VTE. It is currently unknown whether the publication of this review led to a change in prescription patterns and a subsequent change in the incidence of VTE in young women.

The aim of this study is therefore to investigate the CHC utilisation and prescribing patterns in a sample of Three European Union Member states (Denmark, United Kingdom, and the Netherlands) in a time period including the completion of the 2013 review and implementation of the resulting recommendations and to estimate any changes in the incidence of VTE between the two periods specified.

This study will provide evidence regarding the necessity of the recommendation to use safer oral contraceptive preparations, as it will show whether the implementation of the recommendation was successful and whether it actually affected the incidence of VTE in the target population.

8. Research question and objectives

Was there a change in CHC prescribing patterns between the periods January 2012 – January 2014 and February 2014 – December 2015 and, if so, was there a subsequent change in the incidence rate of VTE?

1. To investigate trends in new user (initiators) prescribing patterns in the two years preceding the relevant Commission Decision (January 2012 – January 2014) and in a similar period following the decision (February 2014– December 2015).
2. To investigate switching patterns between products among prevalent users including reasons for changes (e.g., reimbursement or regulatory and clinical guidance).
3. Within Objectives 1 and 2, to examine any changes in utilisation in groups defined by patient's clinical and demographic risk factors for VTE as detailed in the warnings and contraindications in the European Union Summary of Product Characteristics (SmPC).
4. To examine any differences in the incidence rates of VTE between the two periods specified and, in light of the results for Objective 1-3, to investigate any measurable association between the observed changes in CHC use and changes in the VTE incidence rates.

9. Research methods

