9.1 Study design

Drug utilisation study and epidemiological cohort study using data retrieved from electronic health records from three EU member states, i.e., the Netherlands, Denmark, and the United Kingdom. The study will comprise of seven work packages (WP).

WP1 The Netherlands. Drug utilisation study into prescribing patterns including new use as well as switching between products in the periods before and after implementation of the decision of the European Commission, i.e. January 2012 to January 2014 and February 2014 to December 2015 by using de-identified data obtained through The Dutch Foundation for Pharmaceutical Statistics (SFK), which gathers its data from >95% of community pharmacies in the Netherlands (<https://www.sfk.nl/english>). The drug utilization study described in this WP is descriptive in nature. The outcome will be the number and proportion of women (within each calendar window) initiating different types of oral contraceptives or per switching pattern.

WP2 Denmark. Drug utilisation study into prescribing patterns including new use as well as switching between products in the periods before and after implementation of the decision of the European Commission, i.e. January 2012 to January 2014 and February 2014 to December 2015 by linking data from the following databases: The Danish Civil Registration System (14) (personal identifier, migrations, vital status); and the Danish National Prescription Registry (15) (outpatient dispensations, including date, ATC code, defined daily dose, amount dispensed).

WP3 United Kingdom. Drug utilisation study into prescribing patterns including new use as well as switching between products in the periods before and after implementation of the decision of the European Commission, i.e. January 2012 to January 2014 and February 2014 to December 2015 by using anonymised prescribing data from UK primary care which can be linked to the British National formulary and also to ATC codes.

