We will consider each CHC individually and, additional to the analysis of individual types of combined oral contraceptives, in our analysis, we will group CHC together according to generation (i.e., the second generation containing levonorgestrel/norgestimate and ethinylestradiol, the third generation containing gestodene/desogestrel and ethinylestradiol and the newer generations containing drospirenone and ethinylestradiol).

Analysis

For each calendar year, we provide estimates of the proportion of each oral contraceptive type and the number of switchers (from one type to another or to a different pill strength) overall and stratified by age at initiation of CHC (18-24, 25-29, 30-34, 35-39, 40-44 and 45-49 years).

We will estimate incidence rates of initiating CHC use per 1000 person years at risk including 95% confidence intervals for each calendar year using incident dispensation as the indicator of CHC initiation. Similarly, we will provide estimates of incidence rates of switching per 1000 person years at risk including 95% confidence intervals for each calendar year of the study period.

In order to assess the effects of the review on initiation as well as on switching of treatment (between January 2012- January 2014 and between February 2014- December 2015), we will perform segmented regression analysis, taking the two time periods into account.

For our analyses we will be using SAS version 9.2 or higher.

WP3

Objectives

To obtain the number and proportion of women initiating different types of oral contraceptives in UK between January 2012 to December 2015 and to investigate switching pattern using data from The Health Improvement Network (THIN) primary care database.

Methods

Study population

For the UK drug utilization study, we will make use of anonymised primary care data from when women consult their general practice to obtain oral contraceptives. For each calendar year of the study period (1 January 2012 to 31 December 2015) we will identify women who were between 18 and 49 years and have been registered for at least two years prior with one of the general practices that contributed data to THIN. Individuals with no oral contraceptives prescription prior to study entry (from 2010 onwards) will be followed up until they receive their first oral contraceptive prescription, they become 50 years of age, 31 December 2015, or leave the practice. The new users are defined as women with no prior prescription of CHC in the two years before.

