To investigate switching patterns among prevalent users, individuals will be defined as prevalent users if they had at least one prescription of oral contraceptives between 1 July 2011 and 1 August 2015. Prevalent users will be followed until switch of treatment, six months after last prescription, becoming 50 years of age, December 31st 2015, leave the practice or death, whichever comes first.

Oral contraceptives

We will consider each CHC individually and, additional to the analysis of individual types of combined oral contraceptives, in our analysis, we will group CHC together according to generation (i.e., the second generation containing levonorgestrel/norgestimate and ethinylestradiol, the third generation containing gestodene/desogestrel and ethinylestradiol and the newer generations containing drospirenone and ethinylestradiol).

Analysis

For each calendar year, we provide estimates of the number of initiators of each oral contraceptive type and the number of switchers (from one type to another or to a different dose) overall and stratified by age at initiation of CHC (18-24, 25-29, 30-34, 35-39, 40-44 and 45-49 years), social deprivation (Quintiles of Townsend Deprivation scores), body mass index (BMI) and smoking status.

We will tabulate the estimates of new users by 1000 person years at risk including 95% confidence intervals for each calendar year. Similarly, we will provide estimates of switchers by 1000 person years at risk including 95% confidence intervals for each calendar year of the study period.

In order to assess the effects of the review on initiation as well as on switching of treatment (between January 2012- January 2014 and between February 2014- December 2015), we will perform segmented regression analysis.

For our analyses we will be using Stata version 14 or higher.

WP4

Objectives

To assess changes in the incidence rate of VTE among women using CHCs of reproductive age in the Netherlands between January 2012- January 2014 and February 2014- December 2015 and to investigate any measurable association between these changes and the observed changes in CHC use.

Methods

Study population

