Medication use in the SFK database will be used to approximate the occurrence of VTE by using the first dose of oral anticoagulant, which, in case of DOAC use is specific for VTE or the duration of treatment with Vitamin K antagonists. Incidence of VTE is calculated by following the new users of CHC within each calendar window until they experience a VTE, or up to one year.

We will calculate the incidence among the new users of oral contraceptives in general and per type of oral contraceptive (different types and grouped by generation (second, third and newer generations)).

Analysis

We will tabulate the estimates of the annual incidence of VTE including 95% confidence intervals for each calendar window of the study period.

From segmented regression analysis (WP1), we will obtain information on a potential change in the proportion of initiators of each generation of CHC between January 2012-January 2014 and February 2014- December 2015. Since we have information about the prescription patterns among new users, we can assess whether the changes observed in the proportions of each generation is associated with changes in the incidence rate of VTE in women initiating oral contraceptive use.

Furthermore, we can study the changes in the incidence of VTE within users of different types (and generations) of oral contraceptives. A change in this incidence over time, may indicate that certain preparations are prescribed to low/high risk individuals.

Because we have information about the age and socioeconomic status (risk factors of VTE) of these women, we can stratify analyses on these factors.

For our analysis we will use SPSS for Windows, release 23.0.

WP5

Objectives

To assess changes in the incidence rates of VTE among women of reproductive age overall and by CHC-initiation/switching in Denmark between January 2012-January 2014 and February 2014-December 2015.

Study population

For each calendar year of the study period (1 January 2012 to 31 December 2015) we will identify women who were between 18 and 49 years old. Individuals with no previous record of VTE prior to study entry (from 2002 onwards) will be followed until they are recorded with a VTE, become 50 years of age, 31st of December 2015 or they migrate.

Analysis

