We will estimate the incidence rates of VTE by 10 000 person years at risk in CHC-initiators/switchers before and after the EMA recommendation, including 95% confidence intervals for each calendar year of the study period. We provide overall estimates as well as estimates stratified by age at CHC initiation in oral contraceptive initiators.

For each observation window period (January 2012- January 2014 and between February 2014-December 2015) we will compare the age-standardised incidence rates of VTE against the age standardized VTE incidence rates among initiators/switchers of oral contraceptives in order to evaluate whether overall changes in CHC use is associated with overall changes in incidence of VTE.

Analyses will be performed using SAS version 9.2 or higher.

WP6

Objectives

To assess the incidence rate of VTE among women of reproductive age overall and by initiated CHC in United Kingdom between January 2012- December 2015.

Study population

For the estimate of incidence of VTE in CHC users in UK we will make use of anonymized primary care data. For each calendar year of the study period (1 January 2012 to 31 December 2015) we will identify women who were between 18 and 49 years and have been registered for at least two years prior with one of the general practices that contributed data to THIN. Individuals initiated on CHC with no previous record of VTE prior to study entry (from 2002 onwards) will be followed up until they have their first record of VTE, they become 50 years of age, 31 December 2015 or they de-register with the general practice, whichever comes first.

Analysis

We will tabulate the estimates of incident VTE by 10 000 person years at risk including 95% confidence intervals for each calendar year of the study period among women using CHCs of reproductive age in UK. We provide overall estimates as well as estimates stratified by age, social deprivation (Quintiles of Townsend Deprivation scores), BMI and smoking status.

For each observation window period (January 2012- January 2014 and between February 2014- December 2015) we will calculate the incidence among the new users of oral contraceptives in general and per type of oral contraceptive (different types and grouped by generation (second, third and newer generations)).

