From segmented regression analysis (WP3), we will obtain information on a potential change in the proportion of initiators of each generation of CHC between January 2012-January 2014 and February 2014- December 2015. Since we have information about the prescription patterns among new users, we can assess whether the changes observed in the proportions of each generation is associated with changes in the incidence rate of VTE in women initiating oral contraceptive use.

Furthermore, we can study the changes in the incidence of VTE within users of different types

(and generations) of oral contraceptives. A change in this incidence over time, may indicate that certain preparations are prescribed to low/high risk individuals.

Analysis will be performed using Stata version 14 or higher.

WP7

Outline for the study report

The study report will combine the findings from all 6 work packages. Data from three countries will be used to report on the trends in first ever user prescribing in the two years preceding the relevant Commission Decision January 2012 – January 2014 and the period following the decision February 2014 – December 2015 . Furthermore, using different research strategies, we will report on the changes in the incidences of VTE in the different observation windows, separately for each country. The report will provide evidence regarding the necessity of the recommendation to use safer oral contraceptive preparations as it will show whether the implementation of the recommendation was successful and whether it actually affected the incidence of VTE in the target population.

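### For Denmark and the UK, the Abstract measures changes in CHC use by initiations alone when set against overall VTE; this captures the relevant exposure only incompletely

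*Protocol*

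**What the plan says.** The protocol describes the link between use and VTE differently in different places.

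- **Abstract, Data analysis (Denmark and UK).** Age-standardised VTE incidence is compared "against the age standardised initiations of oral contraceptives in order to evaluate whether overall changes in CHC use is associated" with overall VTE changes. The target is overall use; the measure is initiations.
- **Section 9.2, WP5 (Denmark).** The aim is "To assess changes in the incidence rates of VTE among women of reproductive age overall and by CHC-initiation/switching in Denmark", and the cohort is all women aged 18-49 with no earlier VTE. For the same stated purpose, however, "we will compare the age-standardised incidence rates of VTE against the age standardized VTE incidence rates among initiators/switchers of oral contraceptives". No measure of use enters that comparison.
- **Section 9.2, WP6 (UK).** "Individuals initiated on CHC with no previous record of VTE prior to study entry (from 2002 onwards) will be followed up", and the question is whether the changed generation mix of initiators "is associated with changes in the incidence rate of VTE in women initiating oral contraceptive use". Exposure and outcome refer to the same women.
- **Section 9.2, WP4 (Netherlands).** New users' mix is related to VTE in new users within one year, so the two sides match here as well.

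On the utilisation side, WP2 states "We will estimate incidence rates of initiating CHC use per 1000 person years at risk" and does the same for switching. In WP3, "we provide estimates of the number of initiators of each oral contraceptive type and the number of switchers". WP1 reports new users and switchers. Prevalent users are identified in order to study switching. No work package names the level of current use by product, as prevalence or person-time, as an output.

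**The concern.** VTE among all women of reproductive age depends on how many women are taking CHC at a given time and which products they take. Initiators feed that stock but are only part of it. Two changes could move population VTE while the initiation series stays flat: women stopping CHC, and continuing users moving to other products. Stopping is plausible here, because section 7 says that the decision also drew attention to contraindications. In the other direction, a marked change among initiators may hardly show in population VTE within the 23 months after the decision.

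Objective 4 asks whether changes in CHC use and in VTE are associated, and section 7 and WP7 promise to show whether the recommendation affected VTE in the target population. If the exposure series misses a large part of the relevant change, the reader could see an association where there is none, or miss one that exists.

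**Working it through.** **The plan's own figure.** The only expected VTE count is for Denmark (Abstract, Study size): 300 000 women x 4 years x 4 per 10 000 = 480. It reproduces. The point below disputes no stated figure.

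**Inputs from the protocol**
- Non-users: 2 per 10 000 per year. Lower-risk CHC: 5-7, midpoint 6. Higher-risk CHC: 9-12, midpoint 10.5 (risk table in the Abstract).
- Risk in the first year of use: 8-fold (Abstract, Study size), taken here as 8 x 2 = 16 per 10 000.
- Share of women using oral contraceptives in the UK: 28% (Abstract, Study size), used as the share on CHC. The protocol says only that CHC form a substantial part of it.
- Period after the decision: February 2014 to December 2015, so T = 23/12 = 1.917 years.

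**Assumptions, not in the protocol**
- A share f = 10-20% of users is in the first year.
- Lower- and higher-risk products are split 50/50.
- The ratio 10.5/6 = 1.75 also holds in the first year, giving 11.64 and 20.36 per 10 000 (average 16, difference 8.73).
- Post-decision initiators do not stop within the window.

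**Step 1: population rate.** Continuing users average (6 + 10.5)/2 = 8.25. Rate = 0.28 x [16f + 8.25(1-f)] + 0.72 x 2.
- f = 10%: 0.28 x 9.025 + 1.44 = 3.967 per 10 000
- f = 20%: 0.28 x 9.80 + 1.44 = 4.184 per 10 000

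**Step 2: who carries the VTE.** Letting the continuing-user rate run from 5 to 12, first-year users carry 9-26% of all VTE, continuing users 32-62% and non-users 29-46%. With f = 5-30% the first-year share is 5-36%.

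**Step 3: 10-point shift in initiators' mix from the decision onward.** Averaged over the window, as multiples of f:
- Shifted women still in their first year: (0.5 + 0.917)/1.917 = 0.739
- Shifted women already past it: (0.917²/2)/1.917 = 0.219

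Change = 0.28 x 0.10 x f x (0.739 x 8.73 + 0.219 x 4.5) = 0.28 x 0.10 x f x 7.44.
- f = 10%: 0.0208 / 3.967 = 0.5%
- f = 20%: 0.0416 / 4.184 = 1.0%

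**Step 4: the same shift in all current users.** Change = 0.28 x 0.10 x [8.73f + 4.5(1-f)].
- f = 10%: 0.138 / 3.967 = 3.5%
- f = 20%: 0.150 / 4.184 = 3.6%

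This is 3.6 to 6.6 times the effect in step 3.

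**Step 5: current use falls from 28% to 25%, initiations unchanged.** The women lost are continuing users who become non-users: 0.03 x (8.25 - 2) = 0.1875 per 10 000.
- Without extra first-year risk, the base rate is 0.28 x 8.25 + 1.44 = 3.75 and the change is 5.0%.
- With it, the change is 4.7% (f = 10%) to 4.5% (f = 20%).

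The initiation series shows no change in either case.

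**Step 6: continuing users move from 50% to 30% higher-risk, initiations unchanged in number and mix.** Without extra first-year risk, change = 0.28 x (1-f) x 0.20 x 4.5 / 3.75, which is 6.0% (f = 10%) to 5.4% (f = 20%). The initiation series is again flat, although the planned switching analysis could pick this up.

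**The case against.** **The sentence is confined to the Abstract.** Section 9.2 does not repeat it. WP4 and WP6 relate initiators' mix to initiators' VTE, and switching is analysed in all three countries by segmented regression. This stands and limits the point to the all-women comparison. It does not remove it: WP5 follows all women, and its replacement comparison has no use series.

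**Current use may be available after all.** WP2 reports the proportion of each contraceptive type without restricting it to initiators, and several work packages plan VTE incidence within users of each type, which needs user denominators. So a reader who infers that current use by product is never estimated goes further than the text allows. But the Danish proportion has no stated denominator, and even for all users it gives a mix, not a level, so it cannot show women stopping.

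**Objective 4 refers back to Objectives 1-3,** which concern initiation, switching and risk groups. That is fair, but the Abstract and WP5 both say that they evaluate overall changes in CHC use, which initiation alone does not measure.

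**Initiators matter more than a simple stock-and-flow argument suggests.** This also stands. Ignoring the 8-fold first-year risk would put step 3 at only 0.3-0.6%. The assumed first-year share may also be low: the Study size text says that most users aged 15-25 are starters, and half of 596 565 is already 23% of 1.3 million, although starter is not defined per year and the ages differ from 18-49. At 23% the step 3 effect is 1.1% and the gap to step 4 is 3.2-fold. It is therefore tempting, but wrong, to say that initiations barely reflect the relevant use.

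**Precision is limited.** With 240 cases per period (half of 480), the 95% limits of a rate ratio are exp(±1.96 x √(2/240)) = 0.84 to 1.20. All women would give more cases, but it has not been shown that changes of 3.5-5% could be resolved. The better exposure series corrects what is compared; it does not promise a detectable effect.

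**Conclusion.** The point holds for the Danish and UK comparison in the Abstract and for the all-women comparison in WP5. Initiations reflect only part of the use that drives VTE in all women: about 0.5-1.0% for a 10-point shift in initiators' mix, against about 3.5% if all users shift, and about 5% for a fall in current use that the initiation series would not show.

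These sizes depend on the assumed first-year share and the 50/50 split, on taking 28% as CHC use, and on a non-user rate of 2 per 10 000. The Study size text gives 4 for Danish non-users; with 4, and f = 5-30%, first-year users carry about 7-41% of all VTE.

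A reader might infer that Objective 4 is bound to get a wrong answer. The documents do not support that. It would happen only if the level of use, or continuing users' mix, moved in ways that initiation does not follow and the separate switching analysis does not bring out, and no figure in the protocol shows this. It is a risk worth removing because doing so is cheap.

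**What to change.** 1. Reconcile the Abstract with WP5 and WP6: state, for each country, which exposure series is set against which VTE rate and in which women.
2. For any all-women comparison (WP5, and the UK if the Abstract's sentence is kept), use age-standardised prevalence or person-time of current CHC use, overall and by the risk groups of the Abstract's table.
3. Keep initiations as the exposure only for VTE among initiators, as WP4 and WP6 already do.
4. State the denominator of the Danish proportion of each contraceptive type.

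The data are at hand. The Danish registry holds "outpatient dispensations, including date, ATC code, defined daily dose, amount dispensed", WP2 already uses days supplied to define a switch, and WP3 already ends prevalent users' follow-up six months after the last prescription. The cost is programming of exposure episodes and a stated days-supplied assumption, mainly for the UK. No new data are needed.
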